
A.2 Clinical informatics to Improve Healthcare

Over the last 20 years clinical decision support tools have been implemented through electronic medical record (EMR) systems as a means to improve care delivery and outcomes for a variety of conditions in busy clinical settings.³⁷⁻⁴¹ In this project, we will develop electronic alerts that operate in both Cerner (North Kansas City, MO) and Epic (Verona, WI) platforms, two of the most commonly used EMRs in the U.S. We will build EMR phenotypes that will trigger best practice alerts (BPAs) based on clinical and demographic data available in real time, and we will test the diagnostic accuracy of these phenotypes to identify ED patients with acute gout flares. When an acute gout flare alert is triggered, clinicians can then activate an evidence-based order set and an ED research assistant can be alerted to further evaluate each patient for possible participation in our interventional study and the Gout CORT Registry and Biorepository.

A.3 Scientific Premise

The premise for this project is the known disparities in gout care, a higher prevalence of gout in the Southeast due to disproportionate endemic obesity and comorbidity burden, lack of gout knowledge/educational resources, and a perceived lack of access/adherence to primary and specialty gout care, which leads to

excessive care delivery in the ED. From prior work in osteoporosis management we have found that stories can influence readiness to behavior change and can act as very likely mediator of follow-up visits for care.^{42, 43} Moreover, UAB has proven expertise both in using the ED as a setting for biomedical research and for conducting innovative research to enhance minority patient recruitment into clinical trials.⁴⁴⁻⁵³ The premise for aim 3 of this study is that minority recruitment is low in most studies throughout the US and, under a collaborative NCATS grant aimed at overcoming some of these barriers, we have developed culturally tailored methods we will disseminate in this proposal. Importantly, the current CORT projects that focus on gout mechanisms, genetics, and precision medicine for improving gout outcomes will be enhanced by this proposal are dependent on sufficient phenotypic, genotypic and other patient data as well as having a diversity of participants to markedly improve their generalizability.

A.4 Storytelling as Method to Improve Chronic Disease Care

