Prior to the start of the study, clinical staff working in the UAB ED will participate in sessions where they will be trained and coached to appropriately use the novel gout alert for acute gout (flare) identification. Training will occur during monthly face-to-face meetings and via electronic communication (email, list-serves, social media and study website, short training videos). Since busy ED physicians and staff may fail to recall the details of the study or its purpose in real time, we will build electronic reminders (gout alerts) to notify staff to potential eligibility of patients during the ED visit. We will also generate monthly reports that document the number of patients with potential acute gout flares and compare to the number of patients approached by the on-call research coordinator located in each ED. De-identified reports will be shared with practicing clinicians to provide feedback on performance. UAB deploy over 200 different types of alerts, including drug interaction alerts from the Cerner and Epic systems, including both standard alerts and custom alerts that may be overridden by the clinician users. For this study, we will implement a custom alert than can be overridden at the point of care for the Epic and Cerner systems to identify emergency patients who may be having a gout flare. Administrative billing codes (ICD 10), medications (e.g. urate lowering therapy (ULT) such as allopurinol) and healthcare resource utilization of participants will be captured using structured data in conjunction with keywords in unstructured fields. Using this approach, we will identify patients with an existing gout diagnosis and those newly diagnosed during the index ED visit with gout when the alert is activated.

B.3.1 NLP Algorithm

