The NLP algorithm to create the gout alert in the EMR will be structured and refined with serial pilot testing and chart validation (see B.3.2) initially in the Cerner environment at UAB. We will annotate a set of ED triage chief complaint notes and problem lists for the presence of gout flares and implement a simple algorithm for gout flare ED alerts. The keywords will be used to identify gout patients in the ED possibly experiencing a flare. Patients with a potential acute gout flare will be identified using structured data elements (e.g. prior ICD code for gout) and keywords such as: "gout," "podagra," "monoarthritis," "toe pain" from all data fields in the EMR. These terms shown in Table 1 will be developed as part of the alert development and NLP algorithm. The alert algorithm will be developed iteratively using a gout enriched data cohort until acceptable performance is achieved. Keywords will be normalized using NLP to identify gout patients in the ED possibly experiencing a flare. The algorithm will work on simple Boolean logic and regular expressions and will identify a gout flare based on the presence of a gout keyword to the left of any of the PMH-GAZETEER words OR if there is both a location from the LOCATION-GAZETEER and the gout keyword in the past medical history.

Table 1. Example Description Terms and Gazeteer

GOUT-GAZETEER Case Insensitive	LOCATION-GAZETEER Case Insensitive	LOCATION-GAZETEER Case Sensitive	PMH-GAZETEER Case Insensitive
Gout	toe	knee	LLE
Pain	ankle	wrist	RLE
Tender	foot	feet	LUE
Swelling	thumb	finger	RUE
Swollen	arm	elbow	UE
Stiff	shoulder	hip	LE

The alert algorithm will be developed iteratively in the Cerner environment until acceptable performance achieved. Once acceptable performance is achieved the keywords used and any rules will be provided to other sites as they are identified and approved by the UAB IRB for deployment in the their EHR environments.

B.3.2 Alert Chart Validation

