An alert development dataset will be created by identifying patients at UAB with an ED visit starting in January 2020 and working back until sample size is met. A random sample of 100 charts with an ICD10 code for gout and 50 charts with no ICD10 code for gout (but for whom the alert was triggered) will be identified and reviewed by two trained abstractionists. Data abstraction will look to confirm: 1) a prior history of gout and 2) a gout flare during the time of the ED visit diagnosis; or 3) other potential diagnosis. The review will include past clinic notes for documentation of a diagnosis and clinical features of gout (based on 2015 ACR/EULAR classification criteria for gout), medication lists for drugs used for treatment of gout, review of laboratory and

other diagnostic tests (serum urate and joint fluid urate results), imaging studies consistent with gout diagnosis and management (joint radiographs, ultrasound and CT/MRI) and detailed review of the ED visit to confirm acute gout flare at that time. The abstraction form will be piloted before implementation, and necessary changes will be made. Following abstraction of chart data elements and compilation of the 150 patient dataset by the physician trained research coordinators, two expert rheumatologists will complete a diagnosis confirmation review. In the event there is discordance a third rheumatology clinician will serve as an adjudicator.

B.4 Video Intervention Development

In order to develop the video intervention, a group of patients who are currently successfully managing their gout will be interviewed and asked to tell their stories about the importance of gout care. The overall goal of the gout interviews is to improve patient gout knowledge and encourage actions that will prevent flares, destigmatize gout, and enhance readiness to adopt available long-term treatments including medications, diet, and exercise. Interviews will be conducted to cover a variety of race/ethnicities that might be seen in the ED with gout. Videos will be compiled from these patient interviews as anecdotes taken from these gout patients and presented to people in the ED who are being seen for a potential gout flare. These videos will seek to motivate participants to seek further gout care from their primary physician and the importance of taking ULT medications post-ED discharge.

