The funding announcement we are responding to seeks to improve care and reduce healthcare disparities for chronic disease in the Southeast. Thus, our approach to this study is to maximize the number of patients we can evaluate and improve gout care outcomes. We based our sample size considerations on experience from prior ED interventions, a pilot study conducted at UAB (section C.3.5) aimed at recruiting minority patients for our CORT Registry and Biorepository, based on a prior diagnosis of gout in the UAB EMR, and experience recruiting clinic patients. Annually in the ED, UAB see approximately 720 and 450, gout patients (with primary or secondary diagnoses), respectively. We anticipate identifying approximately 60% of these patients using the alert in real-time ($n = 702$). We also estimate that 80% of the ED physicians will respond to the ED alert and activate the gout order set and referral to the study coordinator (this rate may be improved with approaches discussed in section C.4.4) ($n = 560$). Based on the results of our UAB pilot study (that contacted patients without a known recent flare/acute gout), we anticipate that 50% of these patients will remain eligible (based on medical record review and questionnaire). Thus, we conservatively estimate randomizing a combined total of approximately 280 gout patients annually between UAB. Despite plans to offer compensation for survey completion, we anticipate a 30% rate of survey non-response for the primary outcome at 3 months ($n = 196$, in the per protocol analysis), which we believe will be slightly disproportionate between those receiving the intervention vs. control arm. Based on a sample size of 200 patients and assuming 2:1 randomization in favor of story-telling, the study will have 80% power to detect relative risks of 1.68 or below using a two-tailed Type I error rate of 0.05, assuming the proportion in the control arm scheduling an outpatient primary care or specialist visits targeted for gout within 3 months is above 30% (Figure 4). We picked these rates of visit follow-up visits to represent the range of rates of ED follow-up within 3 months for other conditions such as asthma, stroke, and diabetes. ¹¹¹⁻¹¹⁵

Figure 4. Power for Study Aim 2

C. Adverse Events

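### The live alert's inputs have two different scopes and no time cut-off when the algorithm is replayed on past ED visits, so its sensitivity may be overstated

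*Combined protocol and SAP*

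**What the plan says.** A.2 says that the EMR phenotypes will "trigger best practice alerts (BPAs) based on clinical and demographic data available in real time". B.3 gives the purpose of the alert, which is "to notify staff to potential eligibility of patients during the ED visit". The tool therefore has to work while the visit is in progress.

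B.3.1 describes the input in two ways within one paragraph. For building the algorithm it says: "We will annotate a set of ED triage chief complaint notes and problem lists for the presence of gout flares". For finding patients it names structured elements, with an earlier ICD code as the example, together with keywords drawn "from all data fields in the EMR".

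B.3.2 supplies the charts: "An alert development dataset will be created by identifying patients at UAB with an ED visit starting in January 2020", going backwards in time until enough are found. There are 100 charts with an ICD-10 gout code and 50 without one in which the alert was triggered. Abstractors and rheumatologists then review clinic notes, medications, laboratory results, imaging and the ED visit itself to settle the diagnosis.

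No section states the moment at which the alert fires. None says that, on past visits, the algorithm may read only what had been entered by that moment.

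**The concern.** The chart of a finished visit can hold the ED physician's note, the discharge diagnosis and the visit's own codes. Where these mention gout because the clinician has already diagnosed it, a keyword search that reads them partly scores the clinician's judgement and not the alert's. A live alert that fires earlier would not have that text.

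Two things are at stake. B.8.1 makes the alert's ability to identify gout patients the primary outcome of Aim 1, so sensitivity estimated with later text would not carry over to the working tool. B.3.1 also refines the algorithm repeatedly until its performance is judged acceptable and then passes the keywords and rules to other sites. Terms that succeed only because of later text would go with them.

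**Working it through.** **1. The sections side by side.**
- Intended use (A.2, B.3): live, during the visit.
- Input, first statement (B.3.1): triage complaint notes and problem lists. These are plausibly complete early in the visit.
- Input, second statement (B.3.1): keywords from every EMR field, with no limit by time or encounter.
- Structured input: B.3.1 gives an earlier ICD code as an example only. B.3 also lists ICD-10 billing codes and keywords in unstructured fields, and wants to capture patients first diagnosed at the index visit. It does not say which encounter the codes come from.
- Decision rule (B.3.1): two branches joined by OR. One needs a joint location plus the gout term in the past medical history. The other needs a gout term placed before a word on the history list, with no field or time stated.
- Test material (B.3.2): visits from January 2020 backwards. For 50 of the charts to count as alert-positive, the algorithm must have been run on stored visits.

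It is an inference, though a natural one, that the every-field scope applies to that stored-chart run. B.3.1 does not say so, and nothing in B.3.2 rules it out.

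**2. Direction of the error.** The rule described in B.3.1 fires on the presence of terms, and no term is described that cancels a hit. Under such a rule, more text can only add hits. Sensitivity with later text is therefore at least as high as sensitivity without it.

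Let N be the true flares, E those flagged from entries present at the firing point, and L those flagged only from later entries.
- Replay sensitivity = (E + L) / N
- Live sensitivity = E / N
- Overstatement = L / N
- With f = L / (E + L), live sensitivity = replay sensitivity × (1 − f)

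**3. Size.** The documents give neither a replay sensitivity nor f, so this range is pure assumption. Suppose the replay gave 80%:
- f = 10%: 0.80 × 0.90 = 72%
- f = 20%: 0.80 × 0.80 = 64%
- f = 30%: 0.80 × 0.70 = 56%
- f = 50%: 0.80 × 0.50 = 40%

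If f = 0, there is no overstatement.

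**4. The plan's only performance figure.** B.11 anticipates "identifying approximately 60% of these patients using the alert in real-time". Its funnel reproduces:
- 720 + 450 = 1170
- 1170 × 0.60 = 702
- 702 × 0.80 = 561.6 (stated as 560)
- 560 × 0.50 = 280
- 280 × 0.70 = 196

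The 60% is an expectation for the live alert and is not derived from the B.3.2 charts. It neither measures the overstatement nor falls because of it.

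**The case against.** The strongest reply is that the intent is already clear. A.2 requires live data, the annotated text is triage notes and problem lists, the example code is an earlier one, and one branch of the rule looks in the past history. The every-field sentence describes patients currently in the ED, and a working alert can read only what has been entered when it runs. The full-visit review in B.3.2 belongs to the human reference standard, not to the alert. Serial pilot testing (B.3.1) could expose a live shortfall.

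Much of this stands, and it rules out several stronger readings:
- A reader might infer that the plan searches every field of completed charts. No section says so; that reading joins B.3.1 to B.3.2.
- A reader might infer that no physician note could reach a live alert. No firing time is set, and B.5.1 counts enrolment up to 48 hours after presentation as part of the index visit, so some notes could be visible.
- A reader might infer that accuracy is in fact overstated. No result exists, B.3.2 calls its charts a development set, and B.10.1 does not say that the Aim 1 estimate comes from them.
- A reader might infer a loss of Aim 2 power by putting a lower rate into the B.11 funnel, for example 1170 × 0.50 × 0.80 × 0.50 = 234 randomised a year. That does not follow. The 60% does not come from the chart set; B.2.1 admits patients on the ED physician's diagnosis; B.5.1 lets physician-diagnosed patients return within 48 hours; and section D plans about 168 + 112 = 280 participants, with no section closing accrual after one year.

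The reply does not remove the gap itself. The two scopes differ on whether text written after triage counts, the replay has no cut-off, and the pilot testing is not said to be prospective or to re-estimate accuracy.

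**Conclusion.** The point holds as a risk created by an inconsistent and unbounded input rule. The alert must act live, B.3.1 gives two scopes, and B.3.2 applies the alert to past visits without limiting it to what existed at the firing point. If later index-visit entries are read, the error favours the alert's sensitivity, and the keywords may be fitted to text missing in live use.

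This rests on two assumptions: that the every-field scope is the one programmed for the stored charts, and that in some flares gout is first written after the alert would fire. The size cannot be computed from the documents and could be nil. The percentages in the working only illustrate the formula. No effect on Aim 2 power is claimed. The correction is worth making before any accuracy result is produced.

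**What to change.** In B.3.1 and B.3.2:
- Define the point in the visit at which the alert fires.
- Replace the every-field wording with a list of fields available by then, for example triage complaint, prior problem list, prior ICD codes and prior medications. Reconcile this with the sentence on triage notes and problem lists.
- State that, on past charts, the algorithm reads only entries time-stamped before the firing point, in both development and checking.
- Keep index-visit notes, diagnoses and codes entered after that point for the reference reviewers only.

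The cost is a time-stamp filter in the data pull. No further charts or reviewers are needed. The reported accuracy, sensitivity in particular, may come out lower.

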We propose an integrated and coordinated pathway from the ED to gout continuity of care through primary care and specialty providers. We will leverage innovative recruitment and retention strategies that utilize lay patient navigators at our UAB site, a strategy that was successfully pioneered at UAB by our MHDRC team led by [name] for medical care and research in other disciplines including oncology.^{48, 69-71} Patients classified as having gout based on the 2015 ACR/EULAR criteria^{77, 78} who meet the inclusion/exclusion criteria (noted below) will be randomized 2:1 stratified by race/ethnicity, to the intervention or control arm of this demonstration study. **Figure 1** provides an overview of the study design.

Figure 1. Improving ED Gout Care- Study Design

B.2 Patient Population

B.2.1 Key inclusion criteria

- Meets Gaffo criteria for current gout flare or ED physician diagnosis of acute gout flare
- Adult > 18 years of age,
- Able to communicate and understand English language (a future objective, with additional resources, will include Spanish translation of all study materials).
-

B.2.2 Key exclusion criteria:

- joint complaint related to significant trauma or recent surgery (< 1 month)
- life expectancy of < 6 months,
- current critical illness leading to admission to high acuity medical care unit (ICU, stepdown unit) or requiring surgical intervention (general anesthesia); confirmed septic arthritis or joint infectious arthritis.

B.3 Gout Alert Development and Validation (Aim 1)

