[figure not shown]
B.5.1 Initial Gout Evaluation During Index ED visit and Confirming Eligibility

[figure not shown]
Following the gout alert activation in the ED, research assistants housed in the UAB ED will interview patients in person to further determine possible eligibility, and if potentially eligible, to consider randomization.

Randomization, if approved by the ED physician, will be conducted by the research assistant in the ED using a random number generated programmed on the tablet computer that will serve as the primary interface for the study. If the patient was not enrolled in the study at the index ED visit and the treating physician's diagnosis was acute gout flare; the patient may return to the ED for enrollment in the study no later than 48 hours after presentation to the ED. For the purposes of this study, this is considered part of the index ED visit if the patient

is enrolled within 48 hours of initial presentation to ED. This will also include patients admitted to observation status or in-patient status (excluding ICU and surgical admissions, see exclusion criteria above).

Workflow:

[figure not shown]
B.5.2 Intervention Arm -ED Encounter

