Similar to the intervention arm patients randomized to the control arm at both institutions will be provided with a follow usual care referral to relevant medical services that might benefit their gout under their existing health plan, such as primary care services (if they do not already have a primary care physician) or to the Cahaba Medical Group at the UAB Site. Timing for this planned follow-up will be consistent with typical wait times to see a specialist or general practitioner for their gout. In most US metropolitan areas, given the limited national supply of rheumatologists, the average wait time is 9 to 10 weeks to see a new patient.⁸³ To address the issue of an “attention control,” all persons randomized to the control arm will receive existing educational e-material on the tablet computer on routine preventive health measures including vaccinations and age-appropriate preventive care measures unrelated to gout or the study outcomes. These materials will also be emailed to them.

B.5.4 Gout CORT Registry and Biorepository Sample Collection (Aim 3)

Blood specimens and synovial fluid (if drawn) will be collected for the Gout CORT Registry and Biorepository at the time of the enrollment visit in the ED. Blood specimens and synovial fluid (if collected as part of ED visit) will be collected by ED study coordinators/RAs in PAXGene RNA/DNA tubes and stored in -80° freezer until transport to the UAB Division of Clinical Immunology and Rheumatology for processing and long-term storage (see Shipping Manual). All samples will be labeled with a patient identification (PID) number and date of visit. Documentation of specimens will be stored in the lab computer database, secured and password protected, and distributed to only to authorized personnel. Banked specimens will be available for future research in gout, hyperuricemia, and gout-comorbid conditions (e.g. hypertension, diabetes) and will include samples for genomic DNA, RNA expression, and epigenetic analysis.

B.6 Informed Consent (IC)

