Secondary Outcomes / Covariates				
Social Determinants of Health				
Environmental and social factors	X			
Gout medical care				
Number of gout flares (Gaffo criteria) ^{79, 84}	X	X	X	
Rates of urate lowering therapy (ULT)**	X	X	X	
ULT adherence		X	X	
Opioid prescriptions*	X	X	X	
Weight reduction		X	X	
Healthcare resource utilization (visit number)				
ED visits (indicative of recidivism)*		X	X	
Hospitalizations*		X	X	
Health-related quality of life				
European Quality of Life (EQ-5D) ⁸⁶⁻⁸⁸	X	X	X	
Shared decision making: CollaboRATE scale ⁹⁰		X	X	

* gout follow-up within 3-months of ED visit. ** Assessed through chart or system review

randomized 2:1 stratified by race/ethnicity, to the intervention (storytelling +/- patient navigation) or control arm (usual care). All intervention arm patients in the UAB ED also will be assigned lay navigators to provide personalized support for care transitions and access to post-gout flare medical services needed for preventing recurrent flares.

The following procedures will be completed during the index ED visit:

- Review inclusion/exclusion criteria for registry participation
- Informed Consent
- Review of current/past gout status and medication chart review
- Pain Assessment
- Laboratory
 - Serum uric acid (from chart review)
 - Sample banking
- Survey assessments
 - HRQL
 - SDOH

Laboratory draw will be done in conjunction with ED care blood draw when possible. At the conclusion of visit, participants randomized to navigator arm will be provided navigators picture, contact information, and informed that they will receive a call w/in 72 hours.

B.9.1.2 *Patient Navigator Contact*

72 hours post ED visit

During this initial phone conversation the navigators will: 1) conduct a baseline assessment to identify barriers to attending an outpatient visit for gout care (e.g. transportation) and to adhering to gout treatment recommendations (medications, diet, exercise) and, 2) determine the level of support and assistance (e.g. transportation support) needed by patient. The patient navigator will help facilitate the follow-up visit with a primary care/gout specialist, identify any barriers (e.g. lack of trust in primary care physician or/and healthcare system), and provide institutional/community resources that can be mobilized for the patient.

4 weeks post ED visit and 24-48 hours prior to appointment (anticipated)

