B.10.3 Secondary Outcome Analyses- Aim 2.

Patient reported outcomes (PROs) and other process of care measures are of key interest in this study. We will examine secondary outcomes using either two-sample t-tests or multiple linear regression models. Distributional assumptions for residuals (normality, homogeneity of variance) will be examined using normal probability plots and residual plots. We will conduct a set of stratified analyses (contrasts) to examine how the between-site differences in approaches affect outcomes. First, comparing across control arms at the four sites we can estimate the impact of the intervention. Second, comparing across intervention arms at the four sites, we can estimate the difference attributable to case manager versus navigators when all individuals receive story telling. We will also examine sex as a biological variable as well as effects of age and race/ethnicity (heterogeneity of treatment effect). We will conduct sensitivity analyses using multiple imputations to account for missing data. While we provide an example sample size for one such measure, the evaluation of these endpoints will be hypothesis-generating only.

B.11 Sample Size Considerations for Aim 2

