Investigational study sites are the University of Alabama at Birmingham and Vanderbilt University Medical center, two large academic medical centers. The study site staff will ensure participants are consented and randomized in accordance with established good clinical research practices. Additionally, site investigators and their staff will be required to have prerequisite human subjects training, and will answer study related questions, as needed.

- University of Alabama at Birmingham (UAB), Birmingham, AL, United States
- Massachusetts General Hospital (MGH), Boston, MA, United States
- MetroHealth Medical Center, Cleveland, OH, United States
- University of Iowa, Iowa City, IA, United States

Approximately n= 168 participants will be enrolled at the UAB site and n = 112 from MGH, MetroHealth, and University of Iowa study sites.

D.1 Participant Recruitment and Consent

The site study staff will:

- Provide participants with adequate information concerning the study procedures, and scope
- Provide adequate opportunity for the participant to consider all available options
- Respond to the participant's questions and concerns
- Ensure that each participant understands all information provided
- Obtain the participant's written voluntary consent to participate
- Sign the consent form as witnesses
- Provide participants with a copy of the consent form

D.2 Participant Retention/Discontinuation

Participants will have the option to withdraw from the study at any time. Study staff will make at least 3 attempts to contact participants for study intervention visits (ie, Patient Navigation at UAB, MGH, MetroHealth,

and University of Iowa) and outcomes assessment surveys at 6 weeks and 3 months. In order to minimize the chances of losing touch with patients, study staff are collecting email addresses and secondary contact names and phone numbers at the original emergency department visit.

If study staff are not able to reach participants after at least 3 phone attempts, they will attempt to reach the secondary contact listed and/or send an email or text message to the participant. Text messages will be sent through the Mosio application, which is an HIPAA-compliant application. If these methods are not successful in contacting participant, then participant will be considered lost to follow up.

D.3 Site Monitoring

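### Site enters neither the stated randomisation strata nor the covariates named for the primary model, so chance site imbalance between arms goes unadjusted in a four-site trial

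*Combined protocol and SAP*

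**What the plan says.** **Allocation.** The design overview (B.1, Aims 1 and 2) says that eligible patients "will be randomized 2:1 stratified by race/ethnicity, to the intervention or control arm of this demonstration study". B.9.1.1 repeats the ratio and the single stratum. B.5.1 has the research assistant randomise in the ED "using a random number generated programmed on the tablet computer". No block size, allocation list or site factor is given.

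**Primary model.** B.10.2 specifies a multivariable logistic regression and gives race, gender and age in brackets as covariates. Site appears in B.10.2 only as a grouping for descriptive statistics.

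**Sites.** Section D plans about 168 patients at UAB and 112 at MGH, MetroHealth and Iowa together.

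**What differs by site.** B.9.1.1 describes storytelling with or without navigation and adds: "All intervention arm patients in the UAB ED also will be assigned lay navigators". B.10.3 speaks of case managers versus navigators. D.2, however, lists "Patient Navigation at UAB, MGH, MetroHealth" and, in the same bracket, Iowa. B.5.2 gives participants at every site a card picturing the navigator team that will contact them. For usual care, the one stated difference is a referral destination, "or to the Cahaba Medical Group at the UAB Site" (B.5.3).

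**Cross-site contrasts.** B.10.3 says that by "comparing across control arms at the four sites we can estimate the impact of the intervention", and that by "comparing across intervention arms at the four sites" the plan can separate case managers from navigators. It calls the evaluation of the secondary endpoints hypothesis-generating.

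**The concern.** The outcome is whether a patient gets to an outpatient gout visit within 3 months. That depends partly on local clinics, waiting times and referral routes, so four health systems may have different background rates even if the intervention is identical everywhere. When site is neither balanced by design nor adjusted for, a chance excess of one site in one arm passes into the estimated treatment effect. At stake is some precision, and how readily the primary result can be defended if the baseline table shows site imbalance.

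**Working it through.** **Inputs from the documents.** 280 patients, of whom 168 (60%) at UAB (section D); 2:1 allocation; 30% non-response, leaving 196 (B.11); power statement of 200 patients, control rate 30%, relative risk 1.68, two-sided 0.05 (B.11).

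**Assumptions not in the documents.** Site gaps in outcome of 10 to 30 points; an even split of the 112 patients over three sites; the same non-response at every site.

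**1. The plan's own power.** The intervention rate is 0.30 × 1.68 = 0.504, a difference of 20.4 points. With 67 controls and 133 intervention patients:
- pooled rate = (67 × 0.30 + 133 × 0.504)/200 = 0.436
- SE under the null = √[0.436 × 0.564 × (1/67 + 1/133)] = 0.0743
- SE under the alternative = √[0.30 × 0.70/67 + 0.504 × 0.496/133] = 0.0708
- power = Φ[(0.204 − 1.96 × 0.0743)/0.0708] = 79.5%

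The stated 80% reproduces.

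**2. Site imbalance without a site stratum.** The SD of the between-arm difference in UAB share is √[0.6 × 0.4 × (1/n₁ + 1/n₂)].

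| | 280 randomised (187/93) | 196 responding (131/65) |
|---|---|---|
| SD of difference in UAB share | 6.2 points | 7.4 points (simulation 7.5) |
| Chance of more than 5 points | about 43% (simulation) | about 50% |
| Chance of more than 10 points | about 11% | about 18% |

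Fixing the overall totals at 187/93 but not stratifying by site gives the same SD, 6.2 points. A small site of about 37 patients expects 12 to 13 controls (95% range 7 to 18). After non-response, a site of about 26 expects about 9 (4 to 13).

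**3. Effect on the primary comparison.** The shift at the 95% limit is the site gap × 1.96 × SD.

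| Assumed gap, UAB v other sites | N = 280 | N = 196 |
|---|---|---|
| 10 points | 1.2 | 1.5 |
| 20 points | 2.4 | 2.9 |
| 30 points | 3.7 | 4.4 |

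These are percentage points, against a design difference of 20.4. For a 20-point gap at N = 196, the SD of the shift is 0.20 × 7.4 = 1.5 points, compared with a standard error of about 7.1 points from step 1. Such a gap explains about 0.20² × 0.6 × 0.4/0.25 = 4% of outcome variance.

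**4. What each remedy buys.** With site in the model, each site contributes information in proportion to (intervention × control)/site size. Under unrestricted 2:1 allocation this averages (n − 1) × 2/9 at a site of n, against n × 2/9 with exact balance. Over four sites, the ratio is (280 − 4)/280 = 98.6%, or (196 − 4)/196 = 98.0% among respondents. Once site is in the model, stratifying the allocation by site therefore adds only 1 to 2% of information.

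**5. The cross-site contrasts.** Take UAB against the other sites within one arm, 30% v 50%, N = 196.

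| | Exact 2:1 by site | No site stratum, mean (95% range) |
|---|---|---|
| Intervention arms | 62.6% power | 62.3% (57 to 67%) |
| Control arms | 35.4% power | 35.2% (28 to 42%) |

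Even with perfect balance, the difference detectable with 80% power is about 24 to 25 points in the intervention arms (79 v 52 patients) and 33 to 35 points in the control arms (39 v 26).

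**The case against.** The strongest reply is that this is chance imbalance in a self-described demonstration study. The shift is small beside the design effect, nothing in the documents shows site to be a strong predictor of follow-up, and the 20-point gap is assumed. All of that stands, and it is why the point is minor. It does not explain leaving out of the model a variable that is already recorded.

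Three stronger readings are tempting but not supported.

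- **That the missing stratum materially weakens the B.10.3 site contrasts.** Those contrasts compare different sites within the same arm, so they are not randomised comparisons. Their limits are confounding by site and small numbers. Stratifying by site removes neither, and mean power changes by less than half a point.
- **That the tablet method makes the race/ethnicity stratification ineffective.** Stratification does need restricted allocation within strata to balance anything, and no blocking is described. But a number programmed on a tablet is compatible with stratified, blocked lists. The step-by-step guide cited in B.9.1.1 and the workflow figures are not in the available text. If each site's tablet ran its own blocked list, allocation would already be stratified by site in effect. The method is unreported, not shown to be absent.
- **That the intervention differs by site.** B.9.1.1 and B.10.3 point that way; B.5.2 (the navigator card) and D.2 point the other way. For usual care, only the UAB referral destination is stated to differ.

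**Conclusion.** The concern holds in a limited form. Neither the stated allocation nor the named primary-model covariates deal with site. The cost is modest noise: the UAB share is more than 10 points apart between arms in about 11% of trials of 280, and under an assumed 20-point site gap the unadjusted difference shifts by up to about 2.4 to 2.9 points at the 95% limit, against a design difference of 20.4. Randomisation still protects against systematic bias, and the reproduced power statement is not called into question. The size scales directly with the assumed site gap, for which the documents give no figure. The conclusion also assumes that the guide and figures missing from the text do not describe site-specific lists or further covariates. Most of the remedy lies in the analysis model. Site-stratified blocking is good practice with a small extra return.

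**What to change.** 1. In B.10.2, add site (UAB versus other, or four levels) and race/ethnicity as prespecified covariates of the primary logistic model. Site is already recorded, so this costs essentially nothing and can be done at any time before analysis.
2. State the allocation method: whether blocks are used, within which strata, and how the list is concealed. If allocation can still be changed, use concealed permuted blocks of varying size (multiples of 3) within site by race/ethnicity through REDCap, which B.7 already uses for the study data. The cost is an uploaded allocation table. The small downside is that some site-by-race strata will hold few patients. If allocation cannot be changed, explain why site was left out.
3. In B.10.3, label the contrasts across control arms and across intervention arms as non-randomised and subject to confounding by site.
4. Reconcile B.9.1.1 and B.10.3 with B.5.2 and D.2 on which sites provide navigation, so that readers know what the intervention arm contains at each site.
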